10.7 Participant population

The participant populations whose data will be subjected to the trial analysis will be the protocol-compliant population: Any participant who was randomised and received the protocol required trial drug exposure and required protocol processing

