2.1 Assessment and management of risk

Risks related to metformin

The side effects of metformin are mainly gastrointestinal. The relevant summary of product characteristics (SmPC) lists gastrointestinal disorders, such as nausea, vomiting, diarrhoea, abdominal pain and loss of appetite, as very common (frequency $>1/10$). It states that these side effects 'occur most frequently during initiation of therapy and resolve spontaneously in most cases.' Taste disturbance is listed as a common side effect (frequency $>1/100$). All other side effects are described as very rare ($<1/10,000$) or not known (cannot be estimated from available data). In accordance with the SmPC, to minimise gastrointestinal effects as far as possible, the study tablets will be administered after meals, and the dose will be escalated gradually to the target dose.

Hypoglycaemia:

Metformin does not induce low blood sugar levels (hypoglycaemia) when used as the sole glucose-lowering therapy in diabetic patients. It does not exert a hypoglycaemic action in non-diabetic patients unless taken in overdose. Even in the setting of overdose, hypoglycaemia has not been seen with metformin doses up to 85g. As diabetes is an exclusion criterion, the use of other oral glucose-lowering agents will not be permitted in this study.

Although not listed in the SmPC, it is suggested that there may be a risk of hypoglycaemia if metformin is administered in the setting of malnutrition, inadequate caloric intake, or excessive alcohol consumption. Therefore these will be exclusion criteria in this study.

Lactic acidosis:

A predecessor of metformin - phenformin - has been associated with lactic acidosis. However a systematic review published in 2010 evaluated the risk for lactic acidosis in type 2 diabetic patients taking metformin and showed no cases of fatal or nonfatal lactic acidosis in 347 prospective trials and cohort studies with more than 70,490 patient-years of metformin use. The authors concluded that there is no evidence that metformin is associated with an increased risk of lactic acidosis (6).

Metformin and COPD

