3.3 Outcome measures/endpoints

3.4 Primary endpoint/outcome

The median concentration of glucose in sputum in COPD patients after 3 months treatment with metformin compared with 3 months of placebo.

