4 TRIAL DESIGN

The proposed study will be a randomised, double-blinded, placebo-controlled, cross-over study of metformin in patients between the ages of 40 and 75 with a confirmed diagnosis of COPD. It will be an exploratory pilot trial, to gather preliminary information on the effects of metformin on sputum glucose and the feasibility of conducting a full-scale trial.

All subjects will have clinical assessments and blood, airway samples (nasal SAM and sputum) collected at baseline prior to the treatment phase. Clinical assessments will include lung function (FEV₁ and FVC), quality of life and symptom questionnaires (St George's Respiratory Questionnaire, COPD assessment test). Subjects will then either be commenced on metformin or placebo for a period of 3 months and blood, sputum and nasal samples collected at monthly intervals. Following a 2 week washout period the subjects will crossover to the other study arm for another 3 months and repeat samples collected.

Primary Outcome

The primary outcome will be sputum glucose measured using an enzymatic assay (AmplexRed® – ThermoFisher) after 3 months treatment with metformin. There is currently no data on which to base a power calculation and therefore this pilot study will assess what the size of any effect of metformin is in COPD subjects and thereby provide data that can be used to power any future, larger clinical trials.

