7.7 Trial assessments

After baseline assessment, participants will either be commenced on metformin or placebo for 3 months during which time the participants will have monthly visits. At these visits the following assessments will be carried out:

- 1) Collection of data regarding exacerbations and adverse events
- 2) Physical examination
- 3) Blood tests (renal function, liver function tests)
- 4) Lung function
- 5) Sputum samples collected (either spontaneous or induced)
- 6) Nasal SAM strips
- 7) Quality of life/symptom scores

Following a 2 week washout period the subjects will crossover to the other study arm for another 3 months and follow the same study protocol.

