7.10 Withdrawal criteria

Participants will be withdrawn from the trial if:

- 1) They no longer wish to continue in the study and withdraw consent
- 2) They experience a serious adverse event
- 3) They experience an adverse event not related to the study medication that requires them to be withdrawn (e.g. they develop renal or hepatic impairment).

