10 STATISTICS AND DATA ANALYSIS

10.1 Sample size calculation

The primary outcome will be change in sputum glucose from baseline after treatment with metformin, measured using an enzymatic assay (AmplexRed®). The median glucose concentration in COPD subjects measured in our previous study was 1,007 µM (SD 733µM). Metformin reduced airway glucose by c.30% in studies carried out in mice. Therefore to detect a similar effect in humans would require 30 subjects with 90% power at 5% significance. We aim to recruit 40 subjects to account for possible withdrawals.

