10.8 Procedure(s) to account for missing or spurious data

As the study is a small single-centre pilot study with a single primary outcome measure we do not expect missing or spurious data.

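### The only analysis set is selected on compliance after randomisation, with no exposure threshold for that set, and no missing-data method is given although withdrawals are foreseen

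*Combined protocol and SAP*

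**What the plan says.** Section 10.7 defines one population for analysis, which "will be the protocol-compliant population: Any participant who was randomised and received the protocol required trial drug exposure and required protocol processing". The text names no other analysis set, and none for summarising adverse events, although section 9.2 has all of them recorded.

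Section 10.7 does not say how much exposure is required. It also does not say whether a participant who completes one period of the crossover belongs to the set. The one compliance percentage in the protocol, in section 8.11, governs whether a participant may continue in the trial, and 10.7 does not refer to it.

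On missing data, section 10.8 says "we do not expect missing or spurious data", citing the small single-centre design and the single primary outcome. Section 10.1 says "We aim to recruit 40 subjects to account for possible withdrawals", against 30 required. Section 7.10 opens with "Participants will be withdrawn from the trial if" and lists withdrawal of consent, a serious adverse event, and certain unrelated adverse events.

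The primary endpoint in section 3.4 is sputum glucose "after 3 months treatment with metformin compared with 3 months of placebo". Each participant is meant to supply both values: "Following a 2 week washout period the subjects will crossover to the other study arm for another 3 months" (section 7.7).

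**The concern.** Membership of the analysis set is decided by what happens after randomisation. Section 2.1 reports that the product information lists "gastrointestinal disorders, such as nausea, vomiting, diarrhoea, abdominal pain and loss of appetite, as very common", while adding that most cases resolve. Failure to reach the required exposure may therefore be more frequent on metformin than on placebo. If so, exclusion depends on treatment, and the result describes those who tolerated and took the drug rather than everyone randomised to receive it.

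Without a threshold or a per-period rule, two analysts could build different data sets from the same trial. Section 10.8 gives nothing to fall back on when a month-3 value is absent.

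What is at stake is the trial's main product. Section 4 says "this pilot study will assess what the size of any effect of metformin is in COPD subjects", to provide data for powering larger trials, and section 2 says a positive result would justify a trial with exacerbations as the primary outcome. An effect size from compliers alone may not be the right one for that purpose.

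**Working it through.** **1. The plan's own margin.** Inputs from section 10.1: 30 required, 40 recruited. The loss that this margin covers is 1 − 30/40 = 0.25, and 30/(1 − 0.25) = 40. The plan therefore provides for losing up to 10 of 40. It states no withdrawal rate; 25% is only what the margin implies.

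The 30 itself does not follow from the stated inputs alone. With a difference of 0.30 × 1,007 = 302.1 µM and a paired, two-sided 5% comparison, n = (SD of the difference × (1.960 + 1.282) / 302.1)². This gives 62 if the SD of the difference is 733 µM, and 31 if the within-participant correlation is 0.75. That is a separate matter, and nothing below relies on it.

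**2. The passages side by side.**

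- 10.1 over-recruits for withdrawals.
- 7.10 removes some participants from the trial.
- 10.7 keeps only those with the required exposure and processing.
- 10.8 expects no missing data and names no method.

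Together these amount at best to a complete-case analysis that is never stated.

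**3. How far the estimate could move (assumed inputs).** Let f be the share excluded and s the share of the effect that excluded participants have. Take the 30% effect of section 10.1 as the effect in compliers. The all-randomised effect is 0.30 × [(1 − f) + f × s].

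| f | s = 0 | s = 0.5 | s = 1 |
|---|---|---|---|
| 0.10 | 27.0% | 28.5% | 30% |
| 0.25 | 22.5% | 26.3% | 30% |

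On a ratio scale the formula is 1 − exp[(1 − f) × ln 0.70 + f × ln(1 − 0.30 × s)]. With s = 0 it gives 27.5% at f = 0.10 and 23.5% at f = 0.25. The upper value of f is borrowed from step 1 as an assumption; 10.7 states no such share.

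**4. What a wider set can recover.** Taking the endpoint as month-3 glucose (sections 3.4 and 3.7), 40 × 2 = 80 values are scheduled. If 10 participants are excluded, 10 × 2 = 20 values are affected. A wider set recovers:

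- 20 if all ten finished both periods with low exposure;
- 10 if all ten finished only the first period;
- 0 if all ten left before the first month-3 visit.

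**5. What a no-effect sensitivity analysis can show.** Suppose no excluded participant supplies a metformin month-3 value, and each is assigned no effect. The formula in step 3 then returns 0.30 × (1 − f), which is 22.5% at f = 0.25, whatever s really is. The true value under the same assumptions lies anywhere from 22.5% to 30%. The analysis therefore gives a bound and does not correct the estimate. Using the participant's own baseline to represent no effect also assumes no drift on placebo, because the endpoint compares metformin with placebo at month 3.

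**The case against.** **The sections may be coherent.** A reader might infer that 10.8 flatly contradicts 10.1 and 7.10. The documents do not go that far. One can read them as a plan to over-recruit, let withdrawn participants fall outside the compliant set, and analyse about 30, with 10.8 speaking of data within that set. This stands: the fair charge is that 10.8 is too optimistic and the method is only implicit.

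**A compliance figure exists.** A reader might also infer that the protocol has no compliance threshold at all. Section 8.11 does give a percentage. It is a continuation rule, worded as a limit on non-compliance, and 10.7 does not use it, so the gap is the absence of a threshold for the analysis set.

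**The objective is on-treatment, and this is a pilot.** An estimate after three months of actual treatment suits section 3.1, so the compliant set has a place. Even so, it needs a defined threshold, and a trial meant to size an effect should not report it in that set alone.

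**The wider set does not help with early leavers.** This is correct. For participants who leave before month 3 it adds no outcome values, as step 4 of the working shows. The gain is confined to participants who stay, supply a month-3 sample, and would otherwise be dropped.

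**Conclusion.** The point holds as a cheap improvement. As written, the plan restricts the effect estimate to a compliance-selected set that it does not fully define, and it has no stated way of handling missing month-3 values.

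The size is unknown. Under the assumed range, a 30% complier effect corresponds to 22.5% to 30% in all randomised participants. This rests on 10% to 25% being excluded and on their having none to all of the effect.

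A reader might infer that the complier-only result must overstate the effect. The documents do not support that: they give no exclusion rate and no glucose response in non-compliers. They also describe steps to limit gastrointestinal effects, namely dosing after meals and gradual escalation. What they support is that exclusion may depend on treatment and that the two estimates may differ.

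**What to change.** 1. **Section 10.7.** Make the primary set all randomised participants with any available month-3 sputum glucose, analysed by the treatment assigned in that period regardless of compliance, and keep those with one period only. For each secondary endpoint, use all randomised participants with any available data on it. Keep the protocol-compliant set as a sensitivity analysis, with its threshold stated per period and fixed before unblinding. The sponsor must reconcile the wording of 8.11 with the required exposure in 10.7.
2. **Section 10.8.** Delete the statement that no missing data are expected. Report missing month-3 values and their reasons by treatment and period. Say that the wider set recovers only values actually collected. Add one sensitivity analysis that sets missing metformin month-3 values to the participant's own baseline for that period (Appendix 2 schedules sputum at both baselines). Label it a conservative bound, with its assumption of no placebo drift.
3. **Sections 10.3.2 and 10.3.3.** Use a within-participant analysis that can keep one-period participants. An example is a mixed model on log month-3 glucose with treatment and period as fixed effects and participant as random, reported as a ratio with a 95% confidence interval. State its missing-at-random assumption. Reword 10.3.3 so that this model is not carried over to endpoints it does not suit.
4. **Adverse events.** Summarise them in everyone who took at least one dose, by the treatment being taken.

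**Cost.** Wording changes and modest statistician time; no new visits or samples. The downsides are a possibly smaller estimate, and distributional and missing-at-random assumptions that the planned rank test does not make.

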10.8 Procedure(s) to account for missing or spurious data

As the study is a small single-centre pilot study with a single primary outcome measure we do not expect missing or spurious data.

11 DATA MANAGEMENT

11.1 Data collection tools and source document identification

All patient data will be kept on a paper CRF and electronic CRF.

11.2 Data handling and record keeping

CRFs will be kept in a dedicated facility in ICCRU. Each participant will be assigned a unique participant identification code that allows identification of all the data reported for each participant.

11.3 Access to Data

Direct access will be granted to authorised representatives from the Sponsor, host institution and the regulatory authorities to permit trial-related monitoring, audits and inspections in line with participant consent.

11.4 Archiving

Archiving will be authorised by the Sponsor following submission of the end of trial report. All essential documents will be archived for a minimum of 10 years after completion of trial and destruction of essential documents will require authorisation from the Sponsor.

12 MONITORING, AUDIT & INSPECTION

The JRCO via an assigned monitor will establish a monitoring plan which will take in consideration a risk-based approach to determine the monitoring schedule required.

13 ETHICAL AND REGULATORY CONSIDERATIONS

13.1 Research Ethics Committee (REC) review & reports

Before the start of the trial, approval will be sought from a REC for the trial protocol, informed consent forms and other relevant documents. Substantial amendments that require review by REC will not be implemented until the REC grants a favourable opinion for the trial. All correspondence with the REC will be retained in the Trial Master File/Investigator Site File. An annual progress report (APR) will be submitted to the REC within 30 days of the anniversary date on which the favourable opinion was given, and annually until the trial is declared ended. The CI will notify the REC of the end of the trial and if the trial is ended prematurely, the CI will notify the REC, including the reasons for the premature termination. Within one year after the end of the trial, the Chief Investigator will submit a final report with the results, including any publications/abstracts, to the REC and the EU trials register.

13.2 Peer review

The trial was peer reviewed by the funder (Imperial BRC)

13.4 Regulatory Compliance

The trial will not commence until a Clinical Trial Authorisation (CTA) is obtained from the MHRA and Favourable REC opinion. The protocol and trial conduct will comply with the Medicines for Human Use (Clinical Trials) Regulations 2004 and any relevant amendments. The CI will ensure that appropriate approvals from participating organisations are in place.

13.5 Protocol compliance

Prospective, planned deviations or waivers to the protocol will not be allowed. Accidental protocol deviations will be adequately documented on the relevant forms and reported to the CI and Sponsor immediately.

13.6 Notification of Serious Breaches to GCP and/or the protocol

The sponsor will be notified immediately of any case where a serious breach occurs during the trial conduct phase. The sponsor will notify the licensing authority in writing of any serious breach of:
The conditions and principles of GCP in connection with the trial; or
The protocol relating to that trial, as amended from time to time, within 7 days of becoming aware of that breach.

13.7 Data protection and patient confidentiality

All investigators and trial site staff will comply with the requirements of the UK Data Protection Act 2018 with regards to the collection, storage, processing and disclosure of personal information and will uphold the Act's core principles.

Personal information collected will be kept in a secure location in a dedicated facility in ICCRU as stated previously.

Each participant will have a unique, coded, depersonalised identification number.

All clinical samples will be identified with this number.

13.8 Financial and other competing interests for the chief investigator, PIs at each site and committee members for the overall trial management

The investigators have no competing interests that might influence trial design, conduct or reporting.

13.9 Indemnity

Imperial College London holds negligent harm and non-negligent harm insurance policies which apply to this study.

13.10 Amendments

If we wish to make a substantial amendment to the CTA or the documents that supported the original application for the CTA, we will submit a valid notice of amendment to the licencing authority (MHRA) for consideration. If we wish to make a substantial amendment to the REC application or the supporting documents, we will submit a valid notice of amendment to the REC for consideration. Amendments also need to be notified to the R&D office

13.11 Post trial care

On completion of the trial participants will revert to their usual standard of care that currently does not include metformin.

13.12 Access to the final trial dataset

The CI will have access to the final dataset.

14 DISSEMINATION POLICY

14.1 Dissemination policy

On completion of the trial, the data will be analysed and tabulated and a Final Trial Report prepared. The participating investigators will have rights to publish the trial data and the funding body will be acknowledged within the publications. Participants will be notified of the outcome of the trial, if they have requested this.

14.2 Authorship eligibility guidelines and any intended use of professional writers

The investigators will be named as authors. No professional medical writers will be used.

16. APPENDICES

16.1 Appendix 1- Risk

Risks associated with trial interventions

- A ≡ Comparable to the risk of standard medical care
- B ≡ Somewhat higher than the risk of standard medical care
- C ≡ Markedly higher than the risk of standard medical care

Metformin is a licensed medication that has been used extensively for many decades with a well described side effect and safety profile. Therefore in this study that is small, short-term and in which people at a higher risk of adverse effects will be excluded, no new, unexpected adverse effects are expected. Therefore category B is justified.

16.4 Appendix 2 – Schedule of Procedures

Procedures	Visits								
	Screening	Baseline	Treatment Phase						
			Arm 1			Arm 2			
			1 month	2 months	3 months	Baseline	1 month	2 months	3 months
Informed consent	x								
Demographics	x								
Medical history	x								
Physical examination	x	x	x	x	x	x	x	x	x
Vital signs	x	x	x	x	x	x	x	x	x
Concomitant medications	x	x	x	x	x	x	x	x	x
ECG	x								
Laboratory tests	x	x	x	x	x	x	x	x	x
Eligibility assessment	x								
Randomisation		x							
Dispensing of trial drugs		x	x	x		x	x	x	
Compliance		x	x	x	x	x	x	x	x
Blood test		x	x	x	x	x	x	x	x
Sputum sample		x	x	x	x	x	x	x	x
Nasal SAM		x	x	x	x	x	x	x	x
Lung function		x	x	x	x	x	x	x	x
SGRQ		x	x	x	x	x	x	x	x
CAT		x	x	x	x			x	x
Adverse event assessments			x	x	x			x	x

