6.2 Exclusion criteria

Diagnosis of diabetes irrespective of treatment

Diabetes diagnosed on screening bloods

History of hepatic/renal impairment or hepatic/renal impairment diagnosed on screening bloods

Excessive alcohol intake (>21 units/week in males and >14 units in females)

BMI < 18.5kg/m²

Taking metformin irrespective of indication

History of allergy or hypersensitivity to metformin or hypersensitivity or intolerance to any of the placebo compounds

Pregnancy or breastfeeding

Unable to provide informed consent

Any contraindication for Metformin treatment as detailed in Metformin SmPC including:

Acute conditions with the potential to alter renal function such as dehydration, severe infection, shock

Acute or chronic disease which may cause tissue hypoxia such as cardiac or respiratory failure, recent myocardial infarction, shock

Any type of acute metabolic acidosis

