8.4 Drug storage and supply

The IMP will be provided by the supplier (Sharp Clinical Services Ltd) and will be stored at and dispensed from the inpatient pharmacy at St Mary's Hospital. Each subject will be dispensed 1 month's supply when they attend for their baseline visit according to their randomisation code on INFORM. They will then be dispensed 1 month's supply at each of their follow-up monthly visits. Any remaining medication at the end of the study will be collected and counted at the pharmacy who will also be responsible for its destruction.

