8.7 Dosage modifications

N/A

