8.8 Known drug reactions and interaction with other therapies

Concomitant use not recommended:

Alcohol. Alcohol intoxication is associated with an increased risk of lactic acidosis, particularly in cases of fasting, malnutrition or hepatic impairment. Therefore any potential participants with excessive alcohol intake (>21 units/week in males and >14 units in females) will not be recruited.

Iodinated contrast agents. Metformin should be discontinued prior to or at the time of the imaging procedure and not restarted until at least 48 hours, provided that renal function has been re-evaluated and found to be stable.

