9.2 Operational definitions for (S)AEs

As the IMP has a well-known and well established safety profile, new or unreported AEs and ARs are not expected in such a small trial. All AEs and ARs will be recorded. Acute exacerbations are expected to occur in COPD patients and therefore will not be recorded as (S)AEs or ((S)ARs). Breaking the blind will only take place where information about the participant's trial treatment is clearly necessary for the appropriate medical management of the participant

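### The protocol does not say clearly what happens to study drug after a severe exacerbation: 9.2 pulls against 9.1 and 7.10, and no hold rule covers it

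*Combined protocol and SAP*

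**What the plan says.** **Eligibility and dispensing.** Appendix 2 has a row "Eligibility assessment" with one mark, at Screening. Its dispensing row is marked at Baseline and months 1 and 2 of the first arm, and at the same three points of the second. Section 8.4 has the first month's supply given "when they attend for their baseline visit according to their randomisation code on INFORM" and further supplies at the monthly visits. It attaches no clinical condition to either.

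**Contraindications.** Section 6.2 excludes patients with any contraindication in the metformin SmPC. Its examples include "Acute conditions with the potential to alter renal function such as dehydration, severe infection, shock" and "Acute or chronic disease which may cause tissue hypoxia such as cardiac or respiratory failure, recent myocardial infarction, shock".

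**Exacerbations.** Section 9.2 states: "Acute exacerbations are expected to occur in COPD patients and therefore will not be recorded as (S)AEs or ((S)ARs". It sets no limit of severity. Section 7.7 collects exacerbation data at the monthly visits.

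**Stopping drug.** Among the withdrawal criteria in 7.10 is "They experience a serious adverse event". Another covers unrelated adverse events that require withdrawal, with renal or hepatic impairment as the example. Section 8.7, "Dosage modifications", reads N/A. The one written interruption is in 8.8, for iodinated contrast: "Metformin should be discontinued prior to or at the time of the imaging procedure and not restarted until at least 48 hours".

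**Pregnancy.** Section 7 requires a negative urine test before a woman of childbearing potential is included. Section 7.7 lists no later test. Section 8.10 requires contraception throughout, and 9.6 requires pregnancies to be reported within 24 hours of notification.

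**The concern.** The foreseeable acute event in this disease can create a listed contraindication to the study drug. Section 2 says that acute respiratory infections are the main cause of exacerbations and that hospital admission often follows. Section 9.2 itself calls exacerbations expected. Yet the text does not settle whether a participant who has had an exacerbation with respiratory failure or severe infection is withdrawn, held, or simply given the next month's supply.

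The first stake is safety. Appendix 1 justifies risk category B partly on the ground that higher-risk people are kept out, and the only formal check against that list is at Screening. The second is consistency. The number of exacerbations is a secondary endpoint (3.5), and the analysis population in 10.7 depends on drug exposure. If similar events are handled differently from case to case, that affects who contributes data as well as who is protected.

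**Working it through.** The plan states no figure on this point, so there is none to reproduce. The check compares sections and makes a few counts.

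1. **Dispensing against formal checks (Appendix 2).** Dispensing visits: 3 in the first arm + 3 in the second = 6. Formal eligibility assessments: 1, at Screening. Formal re-checks against 6.2 after Screening: 0.

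2. **What is re-checked anyway.** Appendix 2 marks examination, vital signs, concomitant medication and laboratory tests at every visit. Section 7.7 specifies renal and liver function at the monthly visits. Section 9.4 requires adverse event checks whenever participants attend, with ongoing review of risk and benefit. Section 7.10 acts on renal or hepatic impairment. Contraindications that show in these data are largely covered.

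3. **One case followed through the text.** A participant is admitted with an exacerbation and respiratory failure, recovers, and attends the next dispensing visit.
   - *Reading A.* Admission makes the event an SAE under 9.1. Section 7.10 withdraws a participant who experiences an SAE, however it is recorded. Drug stops for good.
   - *Reading B.* Section 9.2 is headed as the operational definition of (S)AEs, so an exacerbation does not count as an AE or an SAE in this trial. Neither event-based criterion in 7.10 is met. Section 8.7 is N/A and 8.8 concerns contrast only. Nothing written stops the next supply.

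   The two readings give opposite results. Neither offers a temporary hold with conditions for restarting.

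4. **Where the gap applies.** Reading B can arise whenever drug is dispensed after an exacerbation, in either sequence. It is not confined to the crossover.

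5. **Why a check at the Arm 2 Baseline is still sensible.** Participants on placebo first take their first metformin 3 months + 2 weeks after Baseline. At 30.4375 days per month this is 3 × 30.4375 + 14 = 105.3 days, plus the unstated interval from Screening. This supports marking a check at that visit; it does not measure the exacerbation gap.

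6. **Pregnancy.** Tests specified after inclusion: 0. The better evidence is the list in 7.7. Appendix 2 has no pregnancy row even at Screening, where section 7 requires a test, so its silence shows little.

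7. **Room for lost participants.** Section 10.1 recruits 40 against a stated requirement of 30, so 40 − 30 = 10 are allowed for all withdrawals.

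**The case against.** The strongest reply is that 9.2 is a recording rule and 7.10 a withdrawal rule. Section 7.10 turns on experiencing an SAE, not on having one recorded, and a hospitalised exacerbation meets 9.1. On that reading the participant is already withdrawn, and a hold with restart would be looser than the present text. This largely stands: Reading A is available, and the documents do not support saying that 9.2 certainly overrides 7.10. But the heading of 9.2 makes Reading B available too, and nothing chooses between them. The point about looseness also stands, and the fix has to respect it.

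A second reply is that other safeguards exist. Section 7.5 allows unblinding for medical reasons, 8.9 requires close renal monitoring if interacting drugs are started, and 8.3 provides the SmPC. Someone in active respiratory failure is unlikely to pass unnoticed through a visit with examination and vital signs. All true, and this keeps the point small. None of these provisions links an exacerbation to the next supply.

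A reader might infer from the single mark in Appendix 2 that nobody is checked again after Screening. Item 2 of the working shows otherwise. A reader might also infer that the problem belongs to placebo-first participants; item 4 shows that it arises in both sequences.

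**Conclusion.** The point holds as a low-cost clarification: worth making, not essential. The protocol leaves unclear whether study drug stops after an exacerbation with respiratory failure or severe infection, and it has no formal re-check against 6.2 at any of the six dispensing visits. Most other contraindications are covered by the repeated assessments and by 7.10.

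The number of participants affected cannot be computed. The documents give no rate of exacerbations or admissions, and only events whose contraindication still applies at dispensing would count. Any headcount would rest wholly on a rate brought in from outside.

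The pregnancy element is marginal. Few women of childbearing potential are likely at age 40 to 85 (6.1), and contraception is already required.

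No effect on sample size, significance level or the primary analysis method is shown. The conclusion rests on 9.2 being open to two readings; if the sponsor confirms that 7.10 governs, one sentence saying so closes the main gap.

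**What to change.** - **7.10 and 8.7.** State that, despite 9.2, study drug is stopped and not dispensed after an exacerbation with respiratory failure or severe infection. Replace the N/A in 8.7 accordingly.
- **Withdrawal or hold.** Say which is meant. If a hold, allow restart only once no 6.2 contraindication remains, and state that this is a deliberate exception to 7.10, so that the rule is not loosened by accident. The clinical thresholds are the sponsor's to set.
- **Every dispensing visit, both sequences.** Apply the rule alike to preserve the blind, using the exacerbation data that 7.7 already collects.
- **Arm 2 Baseline.** Mark a check against the 6.2 contraindications in Appendix 2, based on assessments already scheduled, with one question on exacerbations to cover the washout. As a minor addition, repeat the urine pregnancy test there for women of childbearing potential.

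The cost is a few sentences, a short checklist at existing visits and a urine test for a few women. The downside is that a few participants may miss doses or not enter period 2, and so leave the protocol-compliant population in 10.7. How many cannot be computed; they would draw on the allowance of 10, which must also cover every other withdrawal. A hold with restart should lose fewer than outright withdrawal.
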